14.1.4 Adverse device effects

An untoward medical occurrence that happened in a subject and is related to the device or device procedure (but not the comparator) is an adverse device effect. If the occurrence does not meet the definition of serious, it is classified as an adverse device effect (ADE). Adverse device effects are a subset of adverse events.

14.1.5 Serious adverse device effects

An untoward medical occurrence that happens in a subject, is related to the investigational device, comparator, or procedure, and is serious, but is not unanticipated is a serious adverse device effect (SADE). Untoward medical occurrences that are not unanticipated, i.e. are unsurprising, are identified in the investigator's brochure or protocol and informed consent form.

As with serious adverse events, a serious adverse device effect is one which

- a) Led to a death
- b) Led to a serious deterioration in the health of the subject that:
 - i. Resulted in a life-threatening illness or injury, or
 - ii. Resulted in a permanent impairment of a body structure or a body function, or
 - Required in-patient hospitalization or prolongation of existing hospitalization, or
 - iv. Resulted in medical or surgical intervention to prevent life threatening illness or injury or permanent impairment to a body structure or a body function
 - v. Led to fetal distress, fetal death, or a congenital abnormality or birth defect.

A planned hospitalization for a pre-existing condition or a condition required by the protocol, without serious deterioration in health, is not considered serious.

14.1.6 Unanticipated serious adverse device effect

An untoward medical occurrence that happens in a subject; is related to the investigational device, device procedure, or comparator; is serious; and was unanticipated is classified as an unanticipated serious adverse device effect (USADE). Serious adverse device effect which are *anticipated* are listed below.

14.2 Reporting period

The reporting period includes any adverse events which occurred between randomization and discharge.

14.3 Reporting procedure

All members of the patient management teams will be instructed as to the possible adverse events prior to the start of the trial and will be given an emergency contact number to immediately report any suspected adverse event to the site investigators.

Any possible untoward medical occurrence is identified will be evaluated and classified by the site PI, as follows:

a) Relation to XSTAT device: "Effect" (device-related) vs "event" (device-unrelated)

- b) Seriousness: Serious (meeting the criteria listed above) or not
- c) Anticipated: Anticipated (matching the conditions shown in the list below) or unanticipated

14.3.1 Adverse events (AE)/adverse device effects (ADE)

Adverse events and adverse device effects which are not deemed serious will be recorded using the "PHOXSTAT Adverse Event Recording Form".

14.3.2 Anticipated serious adverse events (SAE)/serious adverse device effects (SADE)

Anticipated adverse device effects include:

- a) XSTAT sponges left in situ after the index operation (either because they cannot be located, or because they were overlooked)
- b) XSTAT sponges which entered the peritoneal or pleural cavities
- c) XSTAT sponge embolization

Anticipated serious adverse events include:

- a) Need for surgical procedure to remove sponges, in the absence of a vascular injury requiring ligation or repair
- b) Death unrelated to XSTAT device
- c) Acute Kidney Injury
- d) Acute Lung Injury/Acute Respiratory Distress Syndrome
- e) Cardiac arrest
- f) Pulmonary embolus
- g) Extremity arterial thrombosis
- h) Multi-organ Failure
- i) Myocardial infarction
- j) Ventilator-Associated Pneumonia

Anticipated serious adverse events and adverse device effects will also be recorded using the "PHOXSTAT Adverse Event Recording Form". In addition, a "PHOXSTAT Serious Adverse Event/Serious Adverse Device Effect" form must be completed, and emailed to the PHOXSTAT Trial Office ([contact]) within 48 hours. All reports of anticipated SAE/SADE will be forwarded to the medical monitor.

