14.1 Definitions and classification

All untoward medical occurrences will be classified by:

- a) Whether they involved a trial participant
- b) Were related to the use of the device
- c) Seriousness
- d) Whether anticipated/unanticipated.

Note that adverse *events* are non-device-related medical occurrences, whereas adverse *effects* are caused by the investigational device or procedure.

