14.1.3 Serious adverse events

Serious adverse events are untoward medical occurrences in a subject that are not related to the investigational device, comparator, or trial procedures, but that meet the criteria of "serious." A serious adverse event is one that:

- a) Led to a death
- b) Led to a serious deterioration in the health of the subject that:
 - i. Resulted in a life-threatening illness or injury, or
 - ii. Resulted in a permanent impairment of a body structure or a body function, or
 - Required in-patient hospitalization or prolongation of existing hospitalization, or
 - Resulted in medical or surgical intervention to prevent life threatening illness or injury or permanent impairment to a body structure or a body function
 - v. Led to fetal distress, fetal death, or a congenital abnormality or birth defect.

A planned hospitalization for a pre-existing condition or a condition required by the protocol, without serious deterioration in health, is not considered serious.

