14.3.3 Unanticipated serious adverse events/serious adverse device effects (USADE)

Unanticipated serious adverse events and adverse device effects will also be recorded using the "PHOXSTAT Adverse Event Recording Form". In addition, a "PHOXSTAT Unanticipated Serious Adverse Event/Serious Adverse Device Effect" form must be completed, and emailed to the PHOXSTAT Trial Office ([contact]) within 48 hours. In addition, the Study PI must be notified, by [contact]) within 48 hours.

On notification of a USAE/USADE report, the PHOXSTAT Trial Office will, within 3 business days:

- a) Forward the report to the medical monitor
- b) Notify the PHOXSTAT DSMB
- c) Notify the UAB IRB
- d) Notify the reporting site's IRB
- e) Notify the DoD (ORP/HRPO, and USAMRMC)

In addition, the PHOXSTAT Trial Office will, within 7 days, notify the FDA, using the MedWatch form.

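### An operation needed only to remove XSTAT sponges is listed among events defined as not device-related, and the matching key outcome has three different definitions

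*Protocol*

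**What the plan says.** **Classification.** Section 14.1 states that adverse events "are non-device-related medical occurrences" and reserves the word effect for occurrences caused by the device or procedure. Section 14.1.3 is stricter: "Serious adverse events are untoward medical occurrences in a subject that are not related to the investigational device, comparator, or trial procedures". Section 14.3(a) tells the site PI to code each occurrence on the same split.

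Section 14.3.2 then gives two lists. The anticipated device effects are three: sponges left behind after the index operation, sponges in the peritoneal or pleural cavity, and sponge embolization. The anticipated serious adverse events are ten, and the first is "Need for surgical procedure to remove sponges, in the absence of a vascular injury requiring ligation or repair".

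**Outcome.** Section 5.2 describes patients treated with XSTAT who prove not to need operative treatment, says they might otherwise have avoided surgery, and calls the number of such explorations a key outcome. Section 7.2.2 says that using the device obliges the team to explore the wound and retrieve the sponges. Section 13.2 names an otherwise unnecessary operation as a risk. Among the safety outcomes, 7.3(f) counts patients with no vascular injury found. The corresponding data item, 8.4.7(f), is non-therapeutic exploration, without further definition. Section 10.3 promises individual and composite incidences of the prespecified events.

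**The concern.** Sponges have to be removed only if XSTAT was deployed. If no vascular injury needs ligation or repair, the operation in 14.3.2(a) is a consequence of the device, and three other sections say so. Its place on the serious adverse event list, read with the protocol's own definitions, tells the person coding the case that it is unrelated.

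The outcome that should measure this harm is also not fixed. The answer to Objective 5 on needless exploration depends on which section the analyst follows. Objective 5 asks whether XSTAT is associated with adverse effects, so both the attribution and the count matter.

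**Working it through.** There is no stated figure to reproduce, so the check compares sections.

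**Step 1: where the item sits.** It appears on 0 of the 3 anticipated device-effect lines and on 1 of the 10 anticipated serious adverse event lines. By 14.1.3 that second list holds occurrences unrelated to device, comparator or trial procedures. By 5.2, 7.2.2 and 13.2 the operation follows from XSTAT use. These statements cannot all hold.

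**Step 2: who is counted.** Sections 5.2 and 8.4.7(f) share the idea of a non-therapeutic exploration, which leaves three substantive definitions.

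| Patient | 5.2 / 8.4.7(f) | 7.3(f) | 14.3.2(a) |
|---|---|---|---|
| XSTAT deployed, explored; vascular injury found that needs no ligation or repair; no other operative treatment | Yes on the 5.2 description; 8.4.7(f) is undefined | No | Yes |
| Device could not be inserted, or control; not explored; no vascular injury found | No | Yes | No |
| Control, explored, nothing found | Yes by the wording of 8.4.7(f); 5.2 describes XSTAT-treated patients | Yes | No, there are no sponges |

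The first two rows are enough. Definition 14.3.2(a) counts the first patient and 7.3(f) does not. Only 7.3(f) counts the second. A further case, with sponges removed, no vascular injury, but another injury needing surgery, separates 5.2 from the other two only if the injury meant in 5.2 includes non-vascular ones. The text does not settle that, so I do not rely on it.

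**Step 3: the base definitions.**
- 14.1.1 limits an untoward medical occurrence to one related to the device, its procedure or the comparator. 14.1.2 then defines an adverse event as such an occurrence that is not related to the device.
- 14.1.4 makes device effects a subset of adverse events, while 14.1 makes the two exclusive.
- 14.1.4 leaves comparator-related occurrences out of device effects. 14.1.5 and 14.1.6 bring them in when serious.

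**Step 4: scale of one case.** Section 9 expects at most 50 patients and no allocation ratio is stated. Assume that 25 receive XSTAT, with a range of 20 to 30. One such operation coded as an event instead of an effect then lowers a device-related rate by 1/25 = 4.0 percentage points (1/20 = 5.0; 1/30 = 3.3). This applies only to a rate restricted to device-related cases. How many cases there will be is unknown.

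**Step 5: can existing data supply one definition?** In the Appendix 2 codebook, the visible operative fields record findings (84 to 88 for wound 1, 100 to 105 for wound 2) and treatment (89 to 93 and 106 to 109). One gap is visible. Field 93, for other operative treatment, is shown only if wound 1 was operated on, or if there is a single wound and the junctional site was operated on. With two wounds and only wound 2 explored it stays hidden, and wound 2 has no counterpart field.

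**The case against.** The strongest reply is that this is loose terminology. The opening of section 14, and sections 10.3, 14.1.4 and 14.2, use adverse event as an umbrella term. The list heading in 14.3.2 does not itself say unrelated, and the next item, a death specified as unrelated to XSTAT, would need no such qualifier if the whole list meant that. This stands as far as it goes: the conflict arises from the definitions, not from the heading. But the definitions are explicit in 14.1, 14.1.3 and 14.3(a).

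Three more points stand.
- Section 10.3 does not split events from effects, so moving the item between lists changes neither the individual nor the composite incidence. Only the competing definitions can change the count.
- Relatedness is a required field on the adverse event form (field 162). Under 14.4 the medical monitor comments on the relationship to trial participation and says whether he or she concurs with the report.
- Section 7.3 already places its version of the outcome under XSTAT safety.

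A reader might infer that a case coded as related and serious, being absent from the effects list, becomes an unanticipated effect and triggers the wider reporting of 14.3.3 ("In addition, the PHOXSTAT Trial Office will, within 7 days, notify the FDA, using the MedWatch form") instead of the route in 14.3.2 ("All reports of anticipated SAE/SADE will be forwarded to the medical monitor"). The text does not support that well. Section 14.1.5 treats an occurrence identified in the protocol as not unanticipated, and this one is identified in several places. Both lists stand under one joint heading, are introduced as non-exhaustive, and 14.3(c) speaks of a single list: "Anticipated (matching the conditions shown in the list below) or unanticipated". The wider route is a possibility that clearer wording would remove.

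A reader might also infer that control patients cannot be recorded, because field 4, which governs the display of later fields, asks about wounds treated with XSTAT. Fields 53 to 83 are not visible, so this cannot be concluded.

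**Conclusion.** The point holds on two counts. First, an operation that the protocol attributes to XSTAT is filed, under the protocol's own definitions, as unrelated to it. Second, a stated key outcome has three substantively different definitions that select different patients. The consequence is limited to device attribution and to the count of this one outcome under Objective 5. Reports reach the Trial Office within 48 hours, and the number of patients affected cannot be computed. The figure of 4 percentage points per case is an illustration that rests on the assumed 25 XSTAT patients.

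The event-code list for field 158, the procedures manual and any SAP are not visible and may define terms. They could choose one definition, but they could not agree with all of these protocol sections at once. The point should be fixed; it is not a threat to patient reporting.

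**What to change.** 1. In 14.3.2, list the sponge-removal item as an anticipated **serious** adverse device effect. The present effects list is not headed serious, so the status must be stated. Keep the site PI's case-level relatedness coding. State in 14.3(c) and 14.1.6 that anticipated refers to both lists, which also covers items such as pulmonary embolus if one is judged device-related.
2. Use one definition of non-therapeutic exploration in 5.2, 7.3 and 8.4.7: operative exploration of the junctional wound at which no injury requiring operative treatment is found. Derive it from the existing finding and treatment fields and report it by arm, without calling it a device effect in controls. Show deaths before any repair separately. The count of patients with no vascular injury found may stay as a separate descriptive item.
3. Reconcile 14.1.1, 14.1.2 and 14.1.4 to 14.1.6 with 14.1: let 14.1.1 cover related and unrelated occurrences, remove the subset sentence in 14.1.4, and treat the comparator the same way throughout.
4. Minor: correct the display rule of field 93 and give wound 2 a counterpart. Confirm that the operative fields display for controls.

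The cost is protocol and code-list wording plus a small eCRF change, with no new measurements. The reported device-related rate may look slightly less favourable.

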14.3.3 Unanticipated serious adverse events/serious adverse device effects (USADE)

Unanticipated serious adverse events and adverse device effects will also be recorded using the "PHOXSTAT Adverse Event Recording Form". In addition, a "PHOXSTAT Unanticipated Serious Adverse Event/Serious Adverse Device Effect" form must be completed, and emailed to the PHOXSTAT Trial Office ([contact]) within 48 hours. In addition, the Study PI must be notified, by [contact]) within 48 hours.

On notification of a USAE/USADE report, the PHOXSTAT Trial Office will, within 3 business days:

- a) Forward the report to the medical monitor
- b) Notify the PHOXSTAT DSMB
- c) Notify the UAB IRB
- d) Notify the reporting site's IRB
- e) Notify the DoD (ORP/HRPO, and USAMRMC)

In addition, the PHOXSTAT Trial Office will, within 7 days, notify the FDA, using the MedWatch form.

14.4 Role and responsibility of the Independent Medical Monitor

An independent medical monitor will review all adverse events/effects and provide an unbiased written report of the events. At a minimum, the medical monitor must comment on the outcomes of the event or problem and in case of a serious adverse event/serious adverse device effect, comment on the relationship to participation in the trial. Because a moderate number of deaths are expected due to the nature of the injuries, individual reports to the PHOXSTAT DSMB will be aggregated and reported on a timely schedule acceptable to the DSMB.

If the death is considered unexpected and is either suspected or probably due to treatment, this event will be promptly reported to the DSMB. The medical monitor must also indicate whether he/she concurs with the details of the report provided by the principal investigator.

[name] is the independent medical monitor for this study. He has committed to comply with the following statements:

The monitor:

- a) Is independent of the research team.
- b) Possesses sufficient educational and professional experience to serve as a subject advocate.
- c) Will promptly report discrepancies or problems to the IRB.

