3. INTRODUCTION

3.1 Background

3.1.1 Trauma is a major public health issue

Trauma is the leading cause of death for people ≤45 years of age and is the third leading cause of death in the United States (US) overall. Trauma accounts for 41 million Emergency Department (ED) visits and 2 million hospital admissions in the US each year, with an economic burden of more than \$585 billion.(1)

Among the injured, hemorrhagic shock is a leading cause of early death, and is responsible for over 35% of prehospital deaths and 40% of deaths within the first 24 hours after injury.(2) Hemorrhage control is of paramount importance in preventing battlefield mortality and is the top priority of the US military.(3) In a study of injuries from Operation Iraqi Freedom and Operation Enduring Freedom, hemorrhage accounted for 82% of potentially survivable casualties.(4)

3.1.2 Junctional bleeding is particularly challenging, and currently available treatments are unsatisfactory

Junctional bleeding is hemorrhage occurring at the junction of two anatomically distinct regions. The PhoXSTAT trial will specifically investigate injuries to the axillary or femoral regions. These injuries are associated with high mortality. A National Trauma DataBank analysis of 120 isolated femoral arterial injuries revealed a mortality rate of 7.5%. (5)

Bleeding from a junctional injury is difficult to control. Currently available treatments include tourniquets, direct and indirect pressure, and hemostatic dressings. These are unsatisfactory (21 CFR 50.24(a)(1)) because

- a) A tourniquet cannot be applied to these body regions: Junctional injuries are too proximal to permit the application of a tourniquet to temporarily occlude blood flow. It is not possible to occlude the iliac (for femoral arterial injuries) or subclavian (for axillary arterial injuries) arteries with a tourniquet.
- b) Indirect pressure on proximal vessels is ineffective. (6) For the same reasons, it is not possible to provide effective digital compression of the iliac or subclavian arteries.

- c) Direct pressure is ineffective, particularly in deep wounds. (6) Penetrating injuries to the junctional vasculature are difficult to control with direct pressure. Inserting digits into these types of wounds can also exacerbate bleeding, by causing further injury to vascular structures.

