14.5 Role and responsibility of the Data and Safety Monitoring Board

The PHOXSTAT DSMB is a distinct and separate entity and functions independently from the sponsor, and the Trial Office. It will be comprised of the following:

- a) [name] (chairman)
- b) [name] (statistician)
- c) [name] (methodologist)

The DSMB has the authority to stop the research in progress, remove individual subjects from the research, and take whatever steps are necessary to protect the safety and wellbeing of the subjects until the IRB can assess its reports.

In addition to reviewing individual reports forwarded by the Independent Medical Monitor, the DSMB will, in conjunction with the trial's biostatistician, conduct interim analyses of the data, at intervals of its choosing. The DSMB will meet at least annually, or more frequently if deemed necessary.

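### Sections 14.1.5, 14.3.2, 14.3.3 and 14.4 do not agree on how a death suspected to be due to the device reaches the DSMB, and one reading lets it be aggregated

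*Protocol*

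**What the plan says.** All references are to the protocol.

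- **Section 14.1.5** defines a serious adverse device effect (SADE) as one that is related, serious and not unanticipated. Its first criterion for seriousness is that the effect led to a death.
- **Section 14.3** has the site PI classify each occurrence by relation to the device, seriousness and anticipation. Anticipation means matching a condition on the list that follows.
- **Section 14.3.2** gives that list. The device effects include "XSTAT sponge embolization", sponges left in place after the index operation, and sponges entering the peritoneal or pleural cavity. The only death listed is "Death unrelated to XSTAT device". Reports go to the Trial Office within 48 hours, and then: "All reports of anticipated SAE/SADE will be forwarded to the medical monitor". No DSMB step is given.
- **Section 14.3.3** covers unanticipated serious events and device effects. Within 3 business days of being notified, the Trial Office informs the medical monitor, the DSMB, the IRBs and the DoD. The FDA is told within 7 days.
- **Section 14.4** opens its passage on deaths with "Because a moderate number of deaths are expected due to the nature of the injuries", and goes on: "individual reports to the PHOXSTAT DSMB will be aggregated and reported on a timely schedule acceptable to the DSMB". The one exception is: "If the death is considered unexpected and is either suspected or probably due to treatment, this event will be promptly reported to the DSMB".
- **Section 14.5** has the DSMB review individual reports forwarded by the medical monitor and run interim analyses at intervals it chooses. On meetings: "The DSMB will meet at least annually, or more frequently if deemed necessary".

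**The concern.** The exception in 14.4 has two conditions joined by *and*: the death must be unexpected, and it must be suspected or probably due to treatment. A death attributed to the device but regarded as expected fails the first condition and falls back to aggregation. Sections 14.1.5 and 14.3.2 show that this category is not empty, because they provide for a device effect that is both fatal and anticipated.

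At stake is how soon the DSMB sees a death attributed to the device. The trial runs under exception from informed consent (Section 6.4). The human evidence the protocol cites is one ten-patient case series (Sections 3.2.4 and 3.3.1), and the DSMB has authority to stop the research (Section 14.5). A death of this kind is one the DSMB needs to see individually and early, and its route should not turn on which line of a list the assessor matches.

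**Working it through.** The routing question is settled by reading the sections together. The only arithmetic concerns what the fix would cost.

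**Test case.** A patient in the XSTAT arm dies after sponge embolization, and the death is judged probably due to the device.

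1. *Related and serious?* Yes to both. Under 14.1.5, leading to a death makes the effect serious.
2. *Anticipated?* Section 14.3 says to match the list in 14.3.2. Two answers are open.
   - **Judged on mechanism.** Embolization is listed, so the effect is anticipated and is a SADE.
   - **Judged on outcome.** The only death listed is one unrelated to the device. A related death is not listed, so the effect is unanticipated.
3. *Route.*

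| Step | Judged on mechanism | Judged on outcome |
|---|---|---|
| Governing section | 14.3.2 | 14.3.3 |
| To Trial Office | 48 hours | 48 hours |
| To medical monitor | Yes, no time stated | Within 3 business days |
| To DSMB | No step in 14.3.2; under 14.4, prompt only if also considered unexpected, otherwise may be aggregated | Within 3 business days |

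4. *Does 14.4 resolve it?* No. It uses the word unexpected, while 14.3 uses anticipated and unanticipated. It does not link the terms or say who decides. If they mean the same, an unexpected treatment-related death is already an unanticipated device effect, and 14.3.3 already takes it to the DSMB. The prompt-report sentence in 14.4 then adds nothing for deaths on the outcome reading, and it leaves out those classed as anticipated on the mechanism reading.
5. *Effect of deleting the condition.* On the outcome reading nothing changes, since the DSMB is notified anyway. On the mechanism reading the gap closes.

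**Number of extra reports.**

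- Inputs: maximum enrolment 50 over two years (Section 9). The only mortality rate given for this type of injury is 7.5% of 120 isolated femoral arterial injuries (Section 3.1.2). The figure is internally consistent: 0.075 × 120 = 9 deaths, and 9/120 = 7.5%.
- Deaths from any cause, both arms: 50 × 0.075 = 3.75. The central 95% range of a binomial with n = 50 and p = 0.075 is 1 to 8.
- XSTAT arm, assuming 1:1 allocation (the ratio is not stated): 25 × 0.075 = 1.9.
- Trial mortality may be higher because class 3 or 4 shock is required (Section 6.2.1). At an assumed 30%, deaths in the XSTAT arm would be 25 × 0.30 = 7.5.

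Deaths suspected or probably due to the device are a subset of the XSTAT-arm deaths. Those that would otherwise have been aggregated are a smaller subset still.

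**The case against.** The case on the other side is substantial, and much of it stands.

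- **There is a second prompt route.** Section 14.4 might be read as the only way a death reaches the DSMB quickly. It is not. Section 14.3.3 covers every unanticipated serious event or device effect, whether or not it is related to treatment.
- **The list leans towards the safer reading.** Naming only unrelated death as anticipated suggests that a related death is unanticipated. This is a fair reading, but matching on the listed condition is equally open, and no sentence chooses between them.
- **The site PI is not the only assessor.** The medical monitor reviews all events, comments on relationship for serious ones, states whether they agree with the investigator's report, and promptly reports problems to the IRB. This reduces the risk, but it does not put the DSMB on the 14.3.2 distribution.
- **The delay has no fixed length.** A reader might infer a wait of up to a year from the annual meeting. That is only the minimum meeting frequency. The aggregate schedule must be timely and acceptable to the DSMB, which may also meet more often, choose its interim analyses and review individual reports forwarded by the monitor.
- **The reason given for aggregation is not refuted.** A reader might set the 7.5% mortality against the expectation of a moderate number of deaths. The documents do not support calling this a contradiction. The rate comes from isolated femoral arterial injuries and is not described as limited to class 3 or 4 shock, and the protocol puts no number on moderate.
- **Stopping authority is not exclusive.** Section 14.5 gives the DSMB authority to stop the research but does not say that no other body has it.

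None of this removes the *and* in 14.4 or the missing rule on mechanism versus outcome.

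**Conclusion.** The point holds as an inconsistency between sections. A device-related death from a listed mechanism can go to the DSMB within 3 business days or be held for an aggregate report, and both routes follow from the protocol's wording. Aggregation is a possible result, not a certain one, and its length cannot be stated because the schedule is left to agreement with the DSMB. The conclusion rests only on the text of 14.1.5 and 14.3 to 14.4. It needs no assumption about mortality or enrolment pace; the death counts above serve only to bound the cost of the fix. The correction is worth making because it closes the gap on one reading and changes nothing on the other.

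**What to change.** 1. In Section 14.4, delete the unexpectedness condition, so that any death suspected or probably due to treatment is promptly reported to the DSMB whether or not its mechanism is on the anticipated list.
2. In Section 14.3.2, add the DSMB to the distribution for device effects with a fatal outcome.
3. Align Section 14.3.3 with this, so that 14.3.2, 14.3.3 and 14.4 give one route and one time limit for such a death.
4. Keep aggregation for deaths judged unrelated.

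The cost is a wording change in three sections and at most a few extra individual reports over the trial. Data collection and analysis are unaffected: Form 12 in Appendix 2 already records relationship, seriousness and anticipation for each event.
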